7.1.6 Excluded Treatments, Medical Devices, and/or Procedures During Study Period

Medications listed below will be proscribed during the study, as these medications are known or suspected to affect bone metabolism:

- strontium (including strontium ranelate and over the counter strontium preparations)
- fluoride (for treatment of osteoporosis)
- Vitamin K and vitamin K analogs (for treatment of osteoporosis)
- Activated vitamin D (1,25-di(OH) vitamin D, or 1 (OH) vitamin D)
- IV bisphosphonates
- oral bisphosphonates (cumulative dosing regimens of ≤ 1 month are acceptable)
- denosumab
- teriparatide or any PTH analogs
- systemic oral or transdermal estrogen (cumulative dosing regimens of ≤ 1 month are acceptable, vaginal preparations and estrogen creams will be allowed at any time)

- SERMs (cumulative dosing regimens of ≤ 1 month are acceptable)
- calcitonin (cumulative dosing regimens of ≤ 1 month are acceptable)
- tibolone (cumulative dosing regimens of ≤ 1 month are acceptable)
- cinacalcet
- prolonged (ie, > 3 months) oral glucocorticoid therapy at a prednisone equivalent dose of ≥ 5.0 mg/day (tapering glucocorticoid courses of ≤ 1 month duration are permitted regardless of dose; inhaled or topical glucocorticoids are permitted)
- hormonal ablation therapy

If a subject discontinues the investigational product and begins an approved alternative osteoporosis therapy, every effort should be made to have the subject continue participation in the study and complete all scheduled assessments (ie, withdrawal of partial consent, see [Section 8](#)).

7.2 Method of Treatment Assignment

Subjects will be randomized in a 1:1 allocation ratio to either the PFS or AI/Pen arm in an open-label manner on a randomization schedule prepared by the Amgen Global Randomization and Blinding Group before the start of the study.

The randomization will be performed by IVRS/IWRS, and the randomization number will be provided through the IVRS/IWRS.

A subject may only be randomized once, and each randomization number may only be assigned once. A subject will be considered enrolled once a randomization number is assigned by the IVRS/IWRS.

The randomization date is to be documented in the subject's medical record and on the enrollment CRF.

7.3 Blinding

This is an open-label study; blinding procedures are not applicable.

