6.3 Subject Enrollment

Before subjects begin participation in any study-specific activities/procedures, Amgen requires a copy of the site's written institutional review board/independent ethics committee (IRB/IEC) approval of the protocol, ICF, and all other subject information and/or recruitment material, if applicable (see [Appendix 3](#)).

The subject or the subject's legally acceptable representative must personally sign and date the IRB/IEC and Amgen approved informed consent before commencement of study-specific procedures.

A subject is considered enrolled when the investigator decides that the subject has met all eligibility criteria. The investigator is to document this decision and date, in the subject's medical record and in/on the enrollment case report form (CRF).

Each subject who enters into the screening period for the study (which begins after the ICF is signed) receives a unique subject identification number before any study-related activities/procedures are performed. The subject identification number will be assigned by the IVRS/IWRS. This number will be used to identify the subject throughout the clinical study and must be used on all study documentation related to that subject.

The subject identification number must remain constant throughout the entire clinical study; it must not be changed after initial assignment, including if a subject is rescreened. This number will not necessarily be the same as the randomization number assigned for the study.

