9.2.2 Efficacy Assessments

9.2.2.1 Dual-energy X-ray Absorptiometry

Bone density measurements will be performed by DXA. Only Lunar or Hologic bone densitometers will be allowed for the study. The same DXA machine must be used for all study procedures for a particular subject for the duration of the study. All DXA scans will be submitted to and analyzed by the central imaging vendor. A separate procedure manual provided by the central imaging vendor will give specific instructions for acquisition of scans as well as performance of Instrument Quality Control.

Bone density will be measured at the lumbar spine and the proximal femur. DXA scans of the lumbar spine will be performed in duplicate, ie, subjects will be removed from the table in between scans. Lumbar spine scans must include L1 through L4. For proximal femur DXA scans, the left side should be used for all scans at all study visits. If the right side must be used (eg, due to implants) or is inadvertently used at baseline, then it must be used consistently throughout the study. If a subject fractures the hip that has been scanned during the study up to the time of fracture, no further scans will be obtained for the affected location.

All DXA scan data will be submitted electronically to the central imaging vendor for analysis. Sites unable to submit data electronically can submit on CD or other media as specified in the DXA Procedural Manual, but electronic submission is preferred.

After analysis by the central imaging vendor, the study site may be asked to re-acquire a scan due to malpositioning or other technical reasons. The investigative sites must comply with the requests from the central imaging vendor. Repeat scans must be performed as soon as possible after the request is received.

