8.4 Detection of Bias

Not Applicable.

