For the post-baseline assessment, if more than 1 visit falls within the defined window, the result from the visit closest to the target day will be used. If 2 evaluations are of the same distance from the target day, the result from the later visit will be used. If more than one evaluation on the same date, the average of the results will be used. Only laboratory results collected from the central laboratory will be averaged in the case of duplicate results.

To allow for variations in scheduling, the following visit windows will be used to assign evaluations to a most appropriate nominal visit for analysis and summarization.

Furthermore, there will be no gaps between visit windows in order to include as many data points as possible for summarization.

Spine and Hip DXA Scans, Physical Measurements^b

Nominal Visit	Target Day	Window Definition (Study Day)
Baseline ^a	1	Last evaluation prior to or on Study Day 1
Month 6	183	≥ Study Day 2

^a If results from baseline DXA are not available, the results from scans taken on or before Study Day 14 will be considered baseline values and not the Month 6 values.

^b Protocol indicates physical measurements will be assessed at month 3, however the data is not collected at month 3.

Serum Romosozumab Levels and Laboratory Assessments (Chemistry)

Nominal Visit	Target Day	Window Definition (Study Day)
Baseline	1	Last evaluation prior to or on Study Day 1
Month 1 ^a	31	Study Day 2 to 61
Month 3	92	Study Day 62 to 137
Month 6	183	≥ Study Day 138

^a Any assessment done on Study Day 1 but after the administration of the investigational product will be classified into Month 1.

Vital Signs, and Laboratory Assessments (Hematology)

Nominal Visit	Target Day	Window Definition (Study Day)
Baseline	1	Last evaluation prior to or on Study Day 1
Month 3	92	Study Day 2 to 137
Month 6	183	≥ Study Day 138

BTMs (sCTX and P1NP)

Nominal Visit	Target Day	Window Definition (Study Day)
Baseline	1	Last evaluation prior to or on Study Day 1
Month 1	31	Study Day 2 to 61
Month 6	183	≥ Study Day 62

Antibody Assessments

Nominal Visit	Target Day	Window Definition (Study Day)
Baseline	1	Last evaluation prior to or on Study Day 1
Month 1 ^a	31	Study Day 2 to 61
Month 3	92	Study Day 62 to 137
Month 6	183	Study Day 138 to 229
Month 9	275	≥ Study Day 230

^a Any antibody assessment done on Study Day 1 but after the administration of the investigational product will be classified into Month 1.

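### Does declaring blinding not applicable leave the central reading of the Month 6 DXA scans, and so the primary endpoint, open to bias?

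*Protocol*

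**What the plan says.** Protocol 7.3 is one sentence: "This is an open-label study; blinding procedures are not applicable". It does not say to whom it applies.

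On the primary measurement, Protocol 9.2.2.1 says: "All DXA scans will be submitted to and analyzed by the central imaging vendor". Once the vendor has analysed a scan, "the study site may be asked to re-acquire a scan due to malpositioning or other technical reasons", and "The investigative sites must comply with the requests from the central imaging vendor". The same section leaves acquisition and instrument quality control to a separate vendor manual, which is not among the documents.

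SAP 8.4, headed Detection of Bias, reads only "Not Applicable".

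On identification and allocation, Protocol 6.3 gives each woman a number when she enters screening and adds: "The subject identification number must remain constant throughout the entire clinical study". Protocol 7.2 states: "The randomization will be performed by IVRS/IWRS". Where several post-baseline evaluations fall in a window, SAP Appendix A states that "the result from the visit closest to the target day will be used". SAP 8.3.1 averages duplicate spine scans taken on the same day.

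**The concern.** Women and site staff cannot be kept from knowing whether a syringe or a pen is used. A remote scan reader can. A blanket statement that blinding does not apply, followed by an empty SAP section on bias, can be read as giving up a protection that was available.

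The vendor also exercises some judgement. It analyses the scans, and a repeat may be sought for technical reasons that are not listed. SAP 8.3 names non-evaluable measurements as a source of missing data, and SAP 9.5.1 analyses observed data only. Decisions on evaluability and repeats therefore help to determine which Month 6 values enter the noninferiority test. If readers knew the arm and leaned towards the pen, a pen that was truly worse by the full margin of 2 points would be declared noninferior more often than the nominal 2.5%.

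**Working it through.** **What the texts establish**

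- *Position of 7.3.* It lies in chapter 7 (Treatments), after Method of Treatment Assignment (7.2) and before Dose Modification (7.4). Its natural subject is the blinding of study treatment. It does not address outcome reading and grants nobody access to assignment.
- *Position of SAP 8.4.* It lies in section 8 (Data Screening and Acceptance), whose aim under 8.1 is to judge the quantity, quality and statistical characteristics of the data. An empty entry there says nothing about what readers know.
- *Other uses of the word 'blind'.* These are the name of the group that prepares the randomization schedule (Protocol 7.2), the masking of identifiers on copied records (Appendix 4) and a field on a safety form (Figure 12-1). None concerns DXA.
- *Route by which the arm could reach a reader.* None is described. The subject number predates randomization and so does not encode the arm. Assignment runs through IVRS/IWRS.
- *Room for influence.* Screening scans are analysed for eligibility before randomization (Protocol 9.1.1.1), so Month 6 scans and their repeats are the main exposure. Each woman stays on one machine (Protocol 9.2.2.1), and only values from the baseline machine type are analysed (SAP 8.3.1). Choice among scans follows the date, not the value.

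**Size, if a bias existed**

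Inputs: SD 4.3 points and 5% dropout (Protocol 10.1); about 130 per arm (Protocol 5.2); margin -2 and one-sided error 0.025 (SAP 9.5.1).

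*The plan's own figure.* The target power is not readable, so 260 cannot be strictly reproduced. Assuming 95% power:

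- n per arm = 2 × 4.3² × (1.960 + 1.645)² / 2² = 120.1, rounded up to 121
- allowing for dropout, 121 / 0.95 = 127.4, rounded up to 128, or 256 in total, close to 260
- assuming 90% or 80% power instead gives 208 or 154

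*Precision.* Evaluable n = 130 × 0.95 = 123.5 per arm. SE = 4.3 × √(2/123.5) = 0.547 points. Power at zero true difference = Φ(2/0.547 − 1.96) = 95.5%.

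*Effect of an assumed mean shift d.* At a true difference of -2, the error is Φ(−1.96 + d/0.547), with d positive when the shift favours the pen. Power at zero true difference is Φ((2 + d)/0.547 − 1.96).

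| Assumed shift d | Error at the margin |
|---|---|
| 0 | 2.5% |
| +0.05 | 3.1% |
| +0.10 | 3.8% |
| +0.20 | 5.5% |
| −0.10 | 1.6% (power falls to 93.5%) |

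None of these shifts has a source in the documents.

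*What a 0.10-point shift would take.* The move per affected woman is 0.10 divided by the affected share of one arm.

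| Share of one arm affected | Women | Move in percent change | Move if only one of two averaged scans is affected |
|---|---|---|---|
| 5% | about 6 | 2.0 points | 4.0 points |
| 10% | about 12 | 1.0 point | 2.0 points |
| 20% | about 25 | 0.5 points | 1.0 point |

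All the moves must run in the same direction and be made by people not shown to know the arm.

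**What new wording would achieve**

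SAP Amendment 1 is dated 08 May 2019 and the primary snapshot was planned for 20 June 2019: 23 + 20 = 43 days. A protocol sentence introduced then could reach few Month 6 reads. Written vendor confirmation, or a table of repeat requests by arm, would put facts on record but alter no estimate, interval or test.

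**The case for a change.** The strongest opposing case is that masking a remote reader costs almost nothing. The protocol presents BMD as an objective measure of successful self-administration (section 3.1), so it should state the safeguard behind that claim. It already takes care over bias in adverse event questioning (9.2.3.1.2) and says nothing comparable about the primary endpoint. One sentence would spare a regulator from relying on unseen vendor papers. If readers did have access to assignment, the sponsor should learn of it before the primary analysis.

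Part of this stands. The readable documents do not state masking, and the description of the vendor manual mentions acquisition and quality control only. Coded identifiers in Appendices 3 and 6 protect confidentiality and are not a promise that assignment is withheld.

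The rest does not carry through to a change. Silence in these two documents does not show that the vendor was told the arm. Masking the reader would leave untouched the sites, which know the arm and acquire the scans. Limiting open-label status in 7.3 to women and site staff would imply that sponsor personnel are masked, which no passage supports. Stating that assignment is withheld would assert something the documents leave unknown.

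**Conclusion.** No change to the plan is needed. What is missing is a statement about reader masking. The documents contain no instruction that exposes readers to assignment, and the primary comparison would still be sound with the plan followed as written. A sentence in Protocol 9.2.2.1, once checked with the vendor, would be harmless tidying and would not affect the analysis.

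Any bias is likely to be small and its direction is unknown. The illustration runs from 3.1% to 5.5% error for assumed shifts of 0.05 to 0.20 points favouring the pen; it measures sensitivity and is not evidence of harm.

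This view assumes that the vendor received no assignment through channels outside the documents and that its manuals follow ordinary central-reading practice. Neither can be confirmed here. Evidence that readers had the assignment would reopen the question.

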7.4 Dose Modification

7.4.1 Dosage Adjustments, Delays, Rules for Withholding or Restarting, Permanent Discontinuation

7.4.1.1 Amgen Investigational Product: Romosozumab

No dosing adjustments for romosozumab will be permitted.

For subjects in the PFS arm, all efforts should be made to administer romosozumab within the defined study visit windows (refer to [Table 2-1](#)). In case of an out-of-window visit, romosozumab can be administered ± 2 weeks of the target visit date, ie, calculated

from the Day 1 visit. If romosozumab cannot be administered \pm 2 weeks of the target visit date, the dose is considered missed.

For subjects in the AI/Pen arm, all efforts should be made to dispense and self-administer the romosozumab AI/Pens within the defined study visit windows (refer to [Table 2-1](#)). In case of an out-of-window visit, AI/Pens can be dispensed and self-administered \pm 2 weeks of the target visit date, ie, calculated from the Day 1 visit. If AI/Pens cannot be dispensed and self-administered \pm 2 weeks of the target visit date, the dose is to be considered missed.

7.4.2 Hepatotoxicity Stopping and Rechallenge Rules

Refer to [Appendix 7](#) for details regarding drug-induced liver injury (DILI) guidelines, as specified in the Guidance for Industry Drug-Induced Liver Injury: Premarketing Clinical Evaluation, July 2009.

7.5 Preparation/Handling/Storage/Accountability

Guidance and information on preparation, handling, storage, accountability, destruction, or return of the investigational product, other protocol-required therapies, or devices during the study are provided in the IPIM for site staff and the Instructions for Use (IFU) document for subjects.

7.6 Treatment Compliance

Subjects in the AI/Pen arm will be asked to bring in all used and unused packages dispensed for their unsupervised self-administration at their next site visit (ie, Month 2, 3, 4, 5, and 6 visits) in a plastic box provided by Amgen. In the case that the subject forgets, he or she should be advised to bring them in at the following site visit. The investigational site staff will count the number of used and unused AI/Pens. The amount dispensed, amount returned, the amount self-administered (ie, full, partial, none, unknown), date dispensed, date returned, the date of self-administration, and box number of romosozumab are to be recorded on each subject's CRF.

7.7 Treatment of Overdose

Overdose with this product has not been reported. Neither the effects of overdose of romosozumab nor an antidote to overdose are known. The maximum amount of romosozumab that can be safely administered in a single dose has not been determined, and there is currently insufficient information to draw any conclusions about the safety of doses higher than those studied in clinical trials. The highest single dose of

romosozumab tested in clinical trials is 10 mg/kg SC. Subjects who have received higher than protocol-defined doses should be carefully monitored for adverse events.

7.8 Prior and Concomitant Treatment

7.8.1 Prior Treatment

Prior therapies affecting bone metabolism that were being taken/used from 5 years prior to screening through randomization will be collected. The therapy name, indication, dose, unit, frequency, start date, and stop date will be recorded.

For the following prior therapies, collect whether the therapy was being taken before screening through randomization: therapies for cardiovascular conditions. The therapy name, indication, dose, unit, frequency, start date, and stop date will be recorded.

A detailed history will also be collected of other prior therapies taken from 30 days prior to study enrollment through randomization. The therapy name, indication, start date, and stop date will be recorded.

7.8.2 Concomitant Treatment

Throughout the study, investigators may prescribe any concomitant medications or treatments deemed necessary to provide adequate supportive care except for those listed in [Section 7.1.6](#).

Concomitant therapies are to be collected from randomization through EOS. For concomitant therapies, collect therapy name, indication, dose, unit, frequency, start date, and stop date.

8. Discontinuation Criteria

Subjects have the right to withdraw from investigational product and/or other protocol-required therapies, protocol procedures, or the study as a whole at any time and for any reason without prejudice to their future medical care by the physician or at the institution.

The investigator and/or sponsor can decide to withdraw a subject(s) from investigational product, device, and/or other protocol-required therapies, protocol procedures, or the study as a whole at any time prior to study completion for the reasons listed in [Sections 8.1, 8.2.1, and 8.2.2](#).

8.1 Discontinuation of Study Treatment

Subjects (or a legally acceptable representative) can decline to continue receiving investigational product and/or other protocol-required therapies or procedures at any time during the study but continue participation in the study. If this occurs, the

investigator is to discuss with the subject the appropriate processes for discontinuation from investigational product or other protocol-required therapies and must discuss with the subject the possibilities for continuation of the Schedule of Activities (see [Table 2-1](#)) including different options of follow-up (eg, in person, by phone/mail, through family/friends, in correspondence/communication with other treating physicians, from the review of medical records) and collection of data, including endpoints, adverse events, disease-related events, and device-related events, as applicable and must document this decision in the subject's medical records. Subjects who have discontinued investigational product and/or other protocol-required therapies or procedures should not be automatically removed from the study. Whenever safe and feasible, it is imperative that subjects remain on-study to ensure safety surveillance and/or collection of outcome data.

Subjects may be eligible for continued treatment with Amgen investigational product(s) and/or other protocol-required therapies by a separate protocol or as provided for by the local country's regulatory mechanism, based on parameters consistent with [Appendix 3](#).

Reasons for removal from protocol-required investigational product(s) or procedural assessments include any of the following:

- Decision by sponsor
- Lost to follow-up
- Death
- Ineligibility determined
- Protocol deviation
- Non-compliance
- Adverse event
- Subject request
- Requirement for alternative therapy
- Pregnancy

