2.2 Schedule of Activities

Table 2-1. Schedule of Activities

PROCEDURE	Screening	Treatment Period							Follow-up	Notes
	up to 35 days before Day 1	Day 1	Month 1 (± 7 days)	Month 2 (± 7 days)	Month 3 (± 7 days)	Month 4 (± 7 days)	Month 5 (± 7 days)	Month 6/ET (-7/+3 days)	Month 9/EOS (-7/+3 days)	
GENERAL AND SAFETY ASSESSMENTS										
Informed consent	X									
Inclusion and exclusion criteria	X									
Demographics	X									
Medical and fracture history	X									
Medication history	X									
Instructions for daily calcium and vitamin D supplementation	X									
Physical examination	X				X			X		
Physical measurements	X				X			X		Height and weight
Vital signs	X				X			X		BP, heart rate, respiratory rate, and temperature
Substance use	X									Substances: alcohol, tobacco, caffeine, other
Adverse events		X	X	X	X	X	X	X	X	
Serious adverse events	X	X	X	X	X	X	X	X	X	
Adverse device effects		X	X	X	X	X	X	X	X	
Disease-related events		X	X	X	X	X	X	X	X	
Concomitant therapies review	X	X	X	X	X	X	X	X	X	

Footnotes defined on last page of the table

Table 2-1. Schedule of Activities

PROCEDURE	Screening	Treatment Period							Follow-up	Notes
	up to 35 days before Day 1	Day 1	Month 1 (± 7 days)	Month 2 (± 7 days)	Month 3 (± 7 days)	Month 4 (± 7 days)	Month 5 (± 7 days)	Month 6/ET (-7/+3 days)	Month 9/EOS (-7/+3 days)	
LABORATORY ASSESSMENTS (CENTRAL)										
Hematology	X	X			X			X		
Serum chemistry	X	X	X		X			X		
Serum 25 (OH) vitamin D	X									One rescreen allowed for vitamin D levels < 20 ng/mL
Hepatitis B and C testing	X									
Serum protein electrophoresis	X									
Anti-romosozumab antibody ^a		X	X		X			X	X	Collect before romosozumab administration
STUDY-SPECIFIC ASSESSMENTS										
DXA scan: lumbar spine	X							X		Perform in duplicate
DXA scan: proximal femur	X							X		
BIOMARKER ASSESSMENTS										
Bone Turnover Markers (sCTX/P1NP)		X	X					X		Obtain from subjects in fasting stage ^b and before noon
PHARMACOKINETIC ASSESSMENTS										
Romosozumab levels		X	X		X			X		
STUDY TREATMENT										
Romosozumab administration ^c										
PFS arm ^d		X	X	X	X	X	X			
AI/Pen arm ^e		X	X	X	X	X	X			
Inquiry on treatment compliance for previous dose				X	X	X	X	X		Collect only from AI/Pen arm

Footnotes defined on next page of the table

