AI/Pen = autoinjector/pen; BP = blood pressure; DXA = dual-energy x-ray absorptiometry; EOS = end of study; ET = early termination; HCP = healthcare provider; P1NP = procollagen type 1 N-telopeptide; PFS = prefilled syringe; sCTX = serum type-1 collagen C-telopeptide

- ^a Subjects who test positive for neutralizing antibodies to romosozumab at the EOS or ET visit will be asked to return for anti-romosozumab antibody testing for up to 1 year after the last investigational product administration. A longer testing period may be requested in the event of safety concerns.
- ^b Fasting stage is defined as overnight or, if not possible, a minimum of 8 hours.
- ^c First dose should be given on day of randomization (or within 72 hours).
- ^d To be administered by site staff as last procedure of each applicable visit.
- ^e As last procedure of Day 1 visit, study staff will supervise self-administration of first dose. At each dosing visit thereafter, the study staff will dispense a single dose (1 box of 2 AI/Pens) to each subject for self-administration without HCP supervision and outside of a professional healthcare facility.

3. Introduction

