8.2.2 Reasons for Removal From Study

Reasons for removal of a subject from the study are:

- Decision by sponsor
- Withdrawal of consent from study
- Death
- Lost to follow-up

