9.5.1 Analyses of Primary Efficacy Endpoint

The primary analysis to assess the percent change from baseline in DXA BMD at lumbar spine at Month 6 will employ an analysis of covariance (ANCOVA) model using observed data. The ANCOVA model will include randomized treatment, baseline value of BMD, machine type, and interaction of baseline BMD value and machine type as prognostic variables. Summaries for the results will include least-squares means point estimates of the percent change from baseline for each treatment arm. The model will allow for heterogeneity between treatments. The 2-sided 95% CI and associated p-value will be provided for the difference between the least-squares means for HCP-administered 210 mg romosozumab by PFS and self-administered 210 mg romosozumab by AI/Pen.

Conclusions for the primary efficacy hypothesis of efficacy of self-administration of romosozumab by AI/Pen compared with HCP-administered romosozumab by PFS at lumbar spine BMD at Month 6 will be made using a 1-sided test with type 1 error rate of 0.025 and noninferiority margin of -2.0%. The primary efficacy analysis set will be used

In addition, summaries of treatment-emergent adverse events occurring in at least 5% of the subjects and serious adverse events occurring in at least 0.1% of the subjects by preferred term in any treatment arm will be provided in descending order of frequency.

Summaries of treatment-emergent and serious adverse events will be tabulated by system organ class, preferred term, and grade.

Subject incidence of disease-related events will be summarized for all treatment-emergent disease-related events and fatal disease-related events by system organ class and preferred term.

The subject incidence of treatment-emergent adverse device effects will also be summarized.

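### Protocol Sections 8 and 8.1 allow undefined non-compliance to end outcome assessment; self-injectors removed without a scan could bias the primary comparison toward noninferiority

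*Protocol*

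**What the plan says.** **Power to withdraw.** The introduction to Protocol Section 8 gives this power to the sponsor and to investigators: either "can decide to withdraw a subject(s) from investigational product, device, and/or other protocol-required therapies, protocol procedures, or the study as a whole", on grounds set out in Sections 8.1, 8.2.1 and 8.2.2.

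**The 8.1 list.** It is headed "Reasons for removal from protocol-required investigational product(s) or procedural assessments include any of the following". Non-compliance, protocol deviation and ineligibility are on it, with no definition or threshold.

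**Retention.** The same section says that, where safe and feasible, "it is imperative that subjects remain on-study to ensure safety surveillance and/or collection of outcome data".

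**Removal from the study.** Section 8.2.2 has its own list, "Reasons for removal of a subject from the study are": sponsor decision, withdrawal of consent, death and loss to follow-up. The three reasons above are absent.

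**Dosing records.** The compliance inquiry in Table 2-1 carries the note "Collect only from AI/Pen arm". For PFS the footnote reads "To be administered by site staff as last procedure of each applicable visit", and Table 7-1 has each PFS dose entered on the CRF.

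**Early termination and analysis.** Protocol 9.1.2 asks subjects who discontinue the study before Month 6 to have the Month 6 procedures, which include the spine DXA. SAP Appendix A assigns any DXA from Study Day 2 onward to Month 6. The primary subset needs a baseline and one post-baseline spine scan and is analysed as randomized. The primary analysis "will employ an analysis of covariance (ANCOVA) model using observed data" (SAP 9.5.1).

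**The concern.** The trial asks whether women can inject themselves successfully at home, with spine BMD as the measure. A woman who misses or spoils home injections is therefore not a nuisance case: her low BMD response is part of the treatment effect. Unsupervised dosing exists in one arm only, and open-label site staff learn of failures while the trial is running.

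If such a woman is taken out of assessments and has no post-baseline scan, she leaves the primary subset. The women lost this way would be low responders in the AI/Pen arm, so the AI/Pen mean would be overstated. In a noninferiority trial that is the anti-conservative direction.

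The supporting analyses that can be read would not correct this:

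- The imputation model (SAP 8.3.1) holds baseline value, machine type and treatment. A removed woman is imputed as if she resembled the scanned women in her arm.
- The per protocol subset (SAP 6.3) requires at least 5 of 6 doses, with partial doses counted as missing, so it excludes the same women by design.
- The disposition table (SAP 9.2) gives reasons for withdrawal from product only, so removal from assessments would not be displayed by reason.

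**Working it through.** **1. Which routes lose the scan?**

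| Route | Early-termination DXA rule (9.1.2) | Effect on the primary analysis |
|---|---|---|
| Stops product, stays in follow-up | Not needed; Month 6 scan is scheduled | In the analysis, correctly |
| Leaves the study, scan done | Applies | In the analysis; an early value stands in for Month 6 and would be expected to lower the AI/Pen mean |
| Leaves the study, scan missed | Applies but not met | Out of the analysis |
| Removed from assessments only | Not covered, because the rule is for those who discontinue the study | Out of the analysis |

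Only the last two rows can push toward noninferiority.

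**2. Inputs.** SD 4.3 points, 5% dropout and true difference 0 (Protocol 10.1); 260 subjects, 1:1 (5.2); margin -2 and one-sided 0.025 (10.3.2.2); six-month spine gain 9.7% (5.4). Assumed, because the documents give no figure: the fraction f of AI/Pen women removed unscanned, and gain proportional to doses taken.

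**3. Check on the plan's size.** The power statement is redacted. At 95% power, n = 2 × (1.960 + 1.645)² × 4.3² / 2² = 120.1, so 121 per arm; 121/0.95 gives 128, or 256 in total against about 260. This is a back-solved consistency check, not a reproduction of a stated power.

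**4. Standard error.** Evaluable per arm: 130 × 0.95 = 123.5. SE = 4.3 × √(2/123.5) = 0.547.

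**5. Shift from unscanned removal.** The shortfall against the AI/Pen women who stay is d = 9.7 × (1 - doses/6): 8.08 after one dose, 4.85 after three. The shift in the AI/Pen mean is f × d. When the true all-randomized difference is exactly -2, the false noninferiority rate is 1 - Φ(1.96 - f × d/SE).

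| f | Doses taken | f × d (points) | Share of margin | Error (nominal 2.5%) |
|---|---|---|---|---|
| 2% (about 2.5 women) | 1 | 0.16 | 8% | 1 - Φ(1.664) = 4.8% |
| 5% (about 6 women) | 3 | 0.24 | 12% | 1 - Φ(1.517) = 6.5% |
| 5% (about 6 women) | 1 | 0.40 | 20% | 1 - Φ(1.221) = 11.1% |

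**6. Cross-check without proportional gain.** Fix the shortfall d against the PFS mean, shrink the AI/Pen sample by f, and set the difference in retained women to -(2 - f × d)/(1 - f). At f = 5%, the error is 3.1% for d = 3, 4.7% for d = 5 and 11.0% for d = 9.7.

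**7. What failures alone could do.** Five per cent one-dose failures create a deficit of only 0.40 points. For failures alone to produce a 2-point deficit, f = 2/8.08 = 24.7%, about 32 of 130 women.

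**The case against.** The case against is substantial.

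- **Early termination.** A woman removed from the study should be scanned, and her scan enters the primary analysis as randomized. That largely closes the study-removal route and reverses the expected direction. It stands. It does not reach assessment-only removal or a missed scan, and an early value is still not the Month 6 endpoint.
- **Retention is the evident intent.** A dose outside the window is simply treated as missed, the CRF records partial or absent home doses with no stated consequence, and Section 7.1.6 wants subjects who switch to another osteoporosis drug followed through all assessments. For subjects found ineligible, Section 9 frames the decision as one about study treatment. This stands as evidence of intent, but no comparable sentence protects the scan of a non-compliant self-injector.
- **The lists can be read separately**, with 8.1 for product and procedures and 8.2.2 for the study. That reading is fair, but the 8.1 heading still reaches assessments, and the Section 8 introduction does not say which list governs which withdrawal.
- **The error rates are conditional.** They need a true difference of exactly -2, most of which would have to come from women who inject correctly, with the same drug and syringe. If the 5% failures were the only cause, the true difference would be -0.40 and a noninferiority conclusion would be correct. This stands.

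A reader might infer that the AI/Pen-only inquiry makes removal one-sided. The documents do not support that: PFS doses are given and recorded by site staff, so missed PFS doses are visible too. The asymmetry lies in unsupervised dosing, not in the inquiry.

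**Conclusion.** The wording conflict is real and should be reconciled: Sections 8 and 8.1 permit what 8.1 itself discourages and 8.2.2 does not list. The statistical consequence is a possible bias toward noninferiority, limited to AI/Pen women removed from assessments only or removed with the early-termination scan missed.

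The illustrated size is 0.16 to 0.40 points, 8% to 20% of the margin, for 2% to 5% of women removed unscanned after one dose. The matching error is 4.8% to 11% at a true difference of exactly -2. This rests on the 9.7% gain, gain proportional to doses, SD 4.3 and 123.5 evaluable per arm. The failure rate and the frequency of such removals are unknown.

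A reader might go further and conclude that the noninferiority result is flattered. The documents do not support that: nothing shows that sites would use the rule this way, and most provisions point toward keeping and scanning these women. The point is a cheap improvement, not a demonstrated flaw in the primary result.

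**What to change.** Three changes to the protocol text:

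1. In Section 8.1, drop the reference to procedural assessments for non-compliance, protocol deviation and ineligibility.
2. In the Section 8 introduction, tie withdrawal from the study to the 8.2.2 reasons.
3. Add a sentence: a missed, partial or incorrect injection, in either arm, is not a reason to omit the DXA. The scan is obtained at the scheduled Month 6 time, where safe and feasible, in every randomized subject who has not withdrawn consent, died or been lost to follow-up.

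The third change matters most. It covers assessment-only removal, and it keeps an early scan from replacing Month 6 in women who are still willing to attend. Decisions about study drug are unchanged.

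The cost is wording, since the Month 6 DXA is already scheduled. The small downside is that a few non-compliant subjects stay in follow-up.
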